6.2.1 Run-in Period

Smoking *ad libitum* will be allowed prior to admission and throughout the day except during the procedures. All subjects will be allowed to continue smoking *ad libitum* their single preferred brand of usual CC. All subjects (except women with a positive pregnancy test at Screening or at Admission) will undergo a THS 2.2 product test prior to enrolment.

Following the confirmation that the subject is able and willing to use the THS 2.2 product, subjects will be enrolled.

6.2.2 Baseline Period

During the baseline period, all subjects will be allowed to continue smoking *ad libitum* their single preferred usual brand of non-menthol CC.

6.2.3 Exposure Period

Subjects will not be allowed to smoke any CC or use any nicotine/tobacco-containing products other than their assigned product/regimen.

6.2.3.1 THS 2.2 Arm

Subjects randomized to the THS 2.2 arm will use exclusively THS 2.2 from Day 1, 06:30 AM onwards until Day 5, 11:00 PM.

6.2.3.2 Conventional Cigarette Arm

Subjects randomized to the CC arm will continue smoking their CC from Day 1, 06:30 AM onwards until Day 5, 11:00 PM.

6.2.3.3 Smoking Abstinence Arm

Subjects randomized to the SA study arm will be instructed to abstain from smoking from Day 1, 06:30 AM onwards until Day 5, 11:00 PM. They will not be provided with medication supportive for smoking abstinence.

6.2.4 Stopping Rules for Investigational Product

For safety purposes, smoking should be temporarily stopped in the event of any signs suggesting nicotine overexposure, (e.g., gastrointestinal disturbance [nausea, vomiting, diarrhea, stomach or abdominal pain], cold sweats, headache, dizziness, and breathing problems) or any reasons at the discretion of the Investigator or designee.

6.2.5 Safety Follow-up Period

During the safety follow-up period (after discharge at Day 6 until Day 13), all subjects are free to smoke their own CC *ad libitum*. Subjects in the SA arm, who wish to continue their SA, or any subject who wish to stop smoking will be referred for further treatment as per the standard of care in the country in which the study is conducted, if requested by the subject.

6.3 Method for Assigning Subjects to Study Arms

When all the eligibility criteria have been met, randomization will be done through the Interactive Web and Voice Response System on Day 0 at any time during the day. Subjects will be informed of their randomized study arm in the morning of Day 1, prior to 06:30 AM.

Subjects will be randomized to one of the 3 study arms: THS 2.2:CC:SA in a 2:1:1 ratio. Stratified randomization will be conducted by sex and by average daily CC consumption in the 4 weeks prior to the Screening Visit as reported by the subject (those smoking 10 to 19 CC and those smoking >19 CC per day). In each arm, each sex and each of the smoking strata should have a quota applied to ensure they represent at least 40% of the population.

6.4 Blinding

This is an open-label study; therefore, the subjects and Investigators or designees will be unblinded to the subject's arm. However, there will be a limited degree of blinding in the data review and data analysis process. In particular, PMI and CRO personnel will be blinded to the randomized arm as summarized in the following table:

| Blinded Study Personnel | End of Blinding Period |
|------------------------------------|--|
| PMI and CRO study statisticians | After the Statistical Analysis Plan (SAP) finalization or PMI blind database review ^(*) , whichever comes last. |
| PMI data manager | After the finalization of PMI blind database review. ^(*) |
| PMI safety and clinical scientists | After the finalization of PMI blind database review ^(*) . Can be actively un-blinded before that time point in case of the occurrence of any safety question, when appropriate. |

Abbreviations: CRO = Contract Research Organization; PMI = Philip Morris International.

(*) As part of the PMI quality control (QC) activity, data listings will be reviewed by PMI before database lock, with no access to the randomization arm information.

Any PMI and CRO personnel who are not listed in the above table will be unblinded by default.

6.5 Investigational Product Accountability and Compliance

6.5.1 Dispensing Investigational Product

From Day-2 onwards, each CC will be dispensed to the subjects. Subjects in the THS 2.2 arm will be provided by the site personnel with Tobacco Sticks from Day 1 to Day 5. One CC/Tobacco Stick will be allowed at a time, as per the study design, and documented in an appropriate log.

On each day of the confinement period, the time of dispense and return for each product (CC/THS 2.2) use has to be documented from Day -1 for CC and from Day 1 for Tobacco Sticks onwards. The subject must not take a puff of the Tobacco Stick during the pre-heating time. The product will not be promoted for commercial distribution or test market.

6.5.2 Storage and Accountability

The THS 2.2 and CC will be stored in a secured storage site with access limited to authorized personnel only. Full accountability of the distributed products will be ensured by designated staff. Subjects will return each butt of CC and any used Tobacco Stick immediately after use. This will be documented in appropriate log.

The filters and tobacco plugs of all used Tobacco Sticks will be collected from Day 1 to Day 5, using dedicated vials for accountability and subsequent analysis of both nicotine and tar assessments in the filters and identification of potential combustion occurrences in the tobacco plugs.

6.5.3 Investigational Product Retention

The study site will destroy or return to the Sponsor any unused Tobacco Sticks and will return to the Sponsor the THS 2.2 product components upon study completion.

Irrespective of the study arm on the time of Discharge from the clinic, the site staff will return to the subjects any remaining CCs given by them on the Day of Admission.

6.5.4 Compliance to Investigational Product(s)

Compliance for all study arms will be ensured by strict distribution of the products (product by product) and collection of Tobacco Sticks, and CC butts will be documented in appropriate log.

In addition, in the SA arm, compliance will be chemically verified using an exhaled CO breath test. The cut-off point for the CO breath test value to distinguish tobacco use vs. no tobacco use will be 10 ppm (Benowitz et al, 2002).

6.6 Restrictions

6.6.1 Smoking Restrictions and Restrictions to the Smoking Abstinence Arm

To avoid cross smoke contamination between the 3 study arms, subjects must use THS 2.2 and CC in separate rooms and subjects allocated to the SA arm should not have access to the smoking rooms. All precautions should be taken to remove any temptation to smoke for subjects who are randomized to the SA study arm.

In the THS 2.2 and SA arms, subjects will not be allowed to smoke any CC or use any nicotine/tobacco-containing products (including NRT) from Day 1 (06:30 AM) until Day 5 (11:00 PM). In CC arm, subjects will not be allowed to use THS 2.2, any nicotine/tobacco-containing products and other CCs than collected to the site by the subject.

During the confinement period, smoking will generally only be allowed during the designated smoking times, from 06:30 AM to 11:00 PM. Subjects will not have free access to their CC or THS 2.2; these will be dispensed by the study site staff individually as described in Section 6.5.1.

Smoking will not be allowed during assessments on the Admission Day at the discretion of the site. Smoking will also not be allowed from Day 5, 11:01 PM until the spirometry has been performed on Day 6.

In general, the performance of scheduled procedures has priority over the wish of a subject to smoke. However, this is different on Day 5 due to the assessment of the nicotine profile. If the subject wants to smoke on Day 5 around the time of the blood draw, he/she should inhale/smoke first and the blood will be drawn after the Tobacco Stick/CC has been inhaled/smoked.

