The exposure period will consist of 5 days of *ad libitum* use of the assigned product between 06:30 AM and 11:00 PM in the THS 2.2 and CC arms. Use of any tobacco/nicotine-containing product other than the assigned product will not be allowed and may, at the discretion of the Investigator or designee, result in the subject withdrawal from the study.

Subjects in the SA arm will be asked to abstain from smoking any nicotine/tobacco-containing product and will not be provided with medication to support SA. Subjects will be provided with psychological support during the period of smoking abstinence.

The end of the 24-hour urine collection period for Day 5 will end in the morning on Day 6 prior to Discharge.

- Day of Discharge (Day 6) (from Day 5, 11:01 PM to time of Discharge):

Procedures of Discharge, including but not limited to laboratory parameters, will be conducted to discharge the subject from the clinic after 9 days in a confined setting. Use of CC will be allowed on Day 6, but only after spirometry has been performed.

- Safety follow-up period (from Day 6, time of Discharge to Day 13):

After time of Discharge, subject will enter a 7-day safety follow-up during which there will be recording of spontaneously reported new adverse events (AEs)/serious adverse events (SAEs) and the active follow-up of ongoing AEs/SAEs by the study site. In general, all AEs will be actively followed until resolved, stabilized (i.e., no worsening of the event), or a plausible explanation for the event has been found. The end of the study is defined as the time of Discharge on Day 6 plus 7-day follow-up period.

During the study, any subjects who want to quit smoking will receive appropriate medical advice and will be referred to a smoking cessation counselor.

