4.1 Overall Study Design and Plan

A randomized, controlled, open-label, 3-arm, parallel group, single-center study with a stratified randomization by sex and average daily CC consumption over the last 4 weeks as reported during the Screening Visit (smokers smoking 10 to 19 CC and smokers smoking >19 CC per day) (Figure S1).

This is an *ad libitum* smoking study. In general, smoking during confinement will be allowed between 06:30 AM and 11:00 PM.

During the confinement period, compliance to product/regimen allocation (exclusive use of THS 2.2 and CC in the THS 2.2 and CC arms respectively, and full abstinence from smoking in the SA arm) will be ensured by strict distribution of each Tobacco Stick/CC on demand of the subject.

Figure S1: Study Design

Abbreviations: THS 2.2 = Tobacco Heating System 2.2; CC = conventional cigarettes.

Confidentiality statement: Data and information contained in this document are considered to constitute trade secrets and confidential commercial information, and the legal protections provided to such trade secrets and confidential information are hereby claimed under the applicable provisions of applicable law. No part of this document may be publicly disclosed without the written consent of Philip Morris Products S.A.

- Screening period over 4 weeks (Day -30 to Day -3) prior to admission to the clinic (Day -2):

A demonstration of the THS 2.2 product will be done by the site staff during the Screening Visit. Subjects will be in a confinement setting for 9 days from Day -2 onwards. Screening procedures do not necessarily have to be conducted on the same day.
- Run-in period (from admission on Day -2 until 06:29 AM of Day -1):

Prior to enrolment on Day -2, as the last procedure of the eligibility assessments, subjects will have a product test of the THS 2.2 (use of up to 3 THS Tobacco Sticks). In female subjects, the THS 2.2 product test may only be done after pregnancy is excluded by a negative urine pregnancy test. Enrolment takes place after all inclusion and exclusion criteria have been satisfactorily met. Only subjects willing and able to use the product will be enrolled in the study.
- Baseline period (from Day -1, 06:30 AM until Day 1, 06:29 AM):

All subjects will continue smoking their single preferred brand of CC and baseline values will be recorded. On Day 0, subjects will be randomized to one of the 3 study arms in a 2:1:1 ratio using a stratified randomization:

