7.5.1.2 Plasma Nicotine and Cotinine

Nicotine and cotinine concentrations will be measured in plasma to evaluate the exposure to nicotine. For subjects in the SA arm, blood samples will be collected on Day 0 to Day 4, at comparable time points. No nicotine PK profile will be done for subjects in the SA arm on Day 5 and Day 6.

- On Day 0 to Day 4 (all study arms):

One blood sample for nicotine and cotinine will be drawn each day 08:00 PM-10:00 PM.

- Nicotine/cotinine PK profile on Day 5 and Day 6 (THS 2.2 and CC arms only):

In total, 9 blood samples will be drawn on Day 5. The first blood sample on Day 5 will be drawn within 15 minutes prior to the first product use (T0). On Day 5, T0 will serve as a reference for the time to peak concentration. An additional 8 blood samples will be drawn in 2 hour intervals after T0. The last blood sample should be drawn no later than 11:00 PM, corresponding to the end of the product use. At all time points, if the subject wants to smoke around the time of the blood draw, he/she should smoke first and the blood will be drawn after the product has been used. Depending on the time of the first product use, it may be that fewer than 8 blood samples will be collected from a subject after T0.

On Day 6, two blood samples will be drawn. The first sample will be 20 hours after T0 and the second blood sample will be 24 hours after T0 (with T0 being the time of the first product use on Day 5).

- On Day 5 and Day 6 (SA arm only):

On Day 5, one blood sample will be drawn 08:00 PM-10:00 PM.

On Day 6, one blood sample will be drawn 08:00 AM-10:00 AM.

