**Table 15. Time Schedule - Day 6**

| Time | Blood sample | Procedures | Additional information |
|---------------------------|--------------|--|--|
| Start of procedure | | Day of Discharge Day 6 | |
| | | AE/SAE recording; concomitant medication | All day until time of discharge |
| | √ | Nicotine, cotinine in plasma | 20 hours and 24 hours blood sampling after T0 of Day 5 for THS 2.2 and CC arms. Each sample has a time window of +/- 5 minutes For SA arm: 08:00 AM-10:00 AM |
| 06:29 AM+/- 30 min | | Analysis sample to be taken after final portion of urine has been added to Day 5 sampling bottle | BoExp, creatinine, and Ames mutagenicity in 24-hour urine Risk markers: 8-epi-PGF2 α and 11-DTX-B2 Bio-banking for BoExp/ risk markers in 24-hour urine (if additional consent is obtained) |
| | | Assessment of cough (VAS) | To be done prior to smoking but not later than 10:00 AM |
| | | MNWS questionnaire | To be done prior to smoking but not later than 10:00 AM |
| | √ | CYP2A6 activity in plasma | To be done prior to smoking |
| | | Spirometry without short-acting bronchodilator | To be done prior to smoking |
| | √ | Clinical laboratory parameters (hematology, clinical chemistry) | To be done after at least 8 hours of fasting |
| | √ | Bio-banking for BoExp/ risk markers in serum/plasma (if consent is obtained) | To be done after at least 8 hours of fasting |
| | √ | Bio-banking for transcriptomics (if consent is obtained) | To be done after at least 8 hours of fasting |
| Before discharge | | Urine safety analysis | |
| Before discharge | | Urine pregnancy test (all females) | |
| before 10:00 AM | | Breakfast | |

Confidentiality statement: Data and information contained in this document are considered to constitute trade secrets and confidential commercial information, and the legal protections provided to such trade secrets and confidential information are hereby claimed under the applicable provisions of applicable law. No part of this document may be publicly disclosed without the written consent of Philip Morris Products S.A.

| Time | Blood sample | Procedures | Additional information |
|------------------|--------------|--|--|
| Before discharge | | CO breath test | |
| Before discharge | | Physical examination, and weight and calculated BMI | |
| Before discharge | | Vital signs (blood pressure, pulse rate, respiratory rate) | At least 5 minutes in supine position prior to measurement |

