7.2 Pharmacokinetic Parameters

The peak nicotine and cotinine plasma concentration (C_{peak}) and time to peak concentration (t_{peak}) will be obtained directly from the concentrations taken on Day 5. The weighted average concentration over 24 hours on Day 5 (C_{avg}) will be calculated by dividing the area under the curve from 0 to 24 h ($AUC_{0-24\text{ h}}$) by 24, where the $AUC_{0-24\text{ h}}$ is calculated using the linear trapezoidal rule.

Since the samples are taken whilst the subjects are smoking freely all samples must be non-missing for the parameters to be calculated as C_{peak} (and t_{peak}) could occur at any time.

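### The Day 6 nicotine/cotinine draws are not required to precede smoking, so own-cigarette nicotine can enter the THS 2.2 24-hour average concentration and the SA Day 6 plasma value

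*Protocol*

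**What the plan says.** **Release to smoking.** Protocol 6.6.1: "Smoking will also not be allowed from Day 5, 11:01 PM until the spirometry has been performed on Day 6". The synopsis, under Day of Discharge, agrees: "Use of CC will be allowed on Day 6, but only after spirometry has been performed". Protocol 4.1 and SAP 6.1 repeat the condition. Protocol 4.1 gives the general smoking hours: "In general, smoking during confinement will be allowed between 06:30 AM and 11:00 PM".

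**Day 6 samples.** Protocol 7.5.1.2, for the THS 2.2 and CC arms: "The first sample will be 20 hours after T0 and the second blood sample will be 24 hours after T0", with T0 the first product use on Day 5. For the SA arm: "On Day 6, one blood sample will be drawn 08:00 AM-10:00 AM". The Table 15 row reads "20 hours and 24 hours blood sampling after T0 of Day 5 for THS 2.2 and CC arms", with a window of 5 minutes either side and the same SA interval. It says nothing about smoking. In the same table, cough, MNWS, CYP2A6 blood and spirometry each carry a before-smoking condition.

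**Use of the samples.** SAP 7.2 defines C_avg as AUC over 0-24 h divided by 24, where the AUC "is calculated using the linear trapezoidal rule". C_peak and t_peak come from the Day 5 concentrations. SAP 12.6.2.3 compares C_avg between THS 2.2 and CC.

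**The concern.** C_avg is meant to describe nicotine and cotinine over the 24 hours that follow the first use of the assigned product. Protocol 6.5.1 provides Tobacco Sticks from Day 1 to Day 5 only, so the one product a THS 2.2 subject may use on Day 6 is a conventional cigarette. If it is smoked before the 24-hour draw, the last point of that subject's curve reflects the comparator product. In the CC arm the same cigarette is the assigned product, so the contamination is off-regimen only in the THS 2.2 arm. In the SA arm, a Day 6 plasma value could show smoking that the protocol itself permitted.

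The wording on smoking around blood draws adds to the uncertainty. Protocol 7.5.1.2, in the part covering the Day 5 and Day 6 profile, tells subjects who want to smoke near a draw to smoke first, at all time points. Protocol 6.6.1 presents this as a Day 5 exception. A site could read either as governing Day 6.

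**Working it through.** The plan states no figure to reproduce. The check has three steps.

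**1. Clock times.** Inputs: smoking hours open at 06:30 AM (Protocol 4.1, assumed to apply on Day 6); spirometry may be done earlier; the 24-hour draw falls on Day 6 at the clock time of T0; up to eight post-T0 Day 5 samples at 2-hour intervals, none later than 11:00 PM (Protocol 7.5.1.2).

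| T0 on Day 5 | Post-T0 samples that fit by 11:00 PM | Smoking time before the 24-hour draw |
|---|---|---|
| 06:30 AM | 8 | 0 min |
| 07:00 AM | 8 | 30 min |
| 08:00 AM | 7 | 90 min |
| 09:00 AM | 7 | 150 min |
| 10:00 AM | 6 | 210 min |

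Eight samples need T0 + 16 h to be no later than 11:00 PM, so T0 by 07:00 AM. The 20-hour draw falls at or before 06:30 AM unless T0 is after 10:30 AM.

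SAP 7.2 calculates the parameters only when all samples are non-missing. If that means all eight, C_avg exists only for T0 by about 07:00 AM, and the opportunity is at most about 30 minutes. Protocol 7.5.1.2 anticipates that late starters will have fewer than eight. If those subjects still get a C_avg, the opportunity runs to hours.

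**2. Weight of the 24-hour sample.** The last trapezoid, from 20 to 24 h, contributes 0.5 × 4 × (C20 + C24) = 2(C20 + C24). An excess D at 24 h adds 2D to the AUC and 2D/24 = D/12 to C_avg. The last interval is 4 h however many Day 5 samples there are, so the weight is always 1/12. The documents give no value for D. For assumed nicotine excesses:

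- D = 5 ng/mL: 5/12 = 0.42 ng/mL
- D = 10 ng/mL: 10/12 = 0.83 ng/mL
- D = 20 ng/mL: 20/12 = 1.67 ng/mL

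**3. Effect on the arms.** If a fraction p of an arm is affected, its mean C_avg rises by pD/12. The THS 2.2 minus CC difference moves by (p_T × D_T − p_C × D_C)/12, where T denotes THS 2.2 and C denotes CC. With an assumed p_T = 25% and no affected CC subjects, the shift is 0.10, 0.21 or 0.42 ng/mL for D = 5, 10 or 20. With equal fractions and excesses in both arms it is zero.

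**The case against.** **A general rule may already cover this.** Protocol 6.6.1 states: "In general, the performance of scheduled procedures has priority over the wish of a subject to smoke". This settles a clash at a given moment. It does not forbid a cigarette between two procedures, for example after spirometry and well before the 24-hour draw.

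**Late starters may never reach the endpoint.** On a strict reading of SAP 7.2, a subject with T0 at 09:00 AM has seven post-T0 samples and no C_avg. This stands, and it limits the opportunity to about 30 minutes. It does not remove it, and the documents do not say which reading applies.

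**The effect may cancel.** The release rule applies to both arms, so CC subjects may also smoke before their draw. This stands for the difference, as step 3 shows, and the size and direction of any net shift are unknown. The THS 2.2 level itself would still include comparator nicotine.

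**Stronger readings.** A reader might infer that other Day 6 arm comparisons are compromised. The documents do not support that:

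- CYP2A6 blood must precede product use (Protocol 7.5.2.3, Table 15).
- Day 5 COHb is drawn on Day 5. The Day 5 urine bottle closes at 06:29 AM, give or take 30 minutes, so it overlaps the smoking hours by 29 minutes at most.
- The SA arm has no PK profile, and the plasma-concentration ANCOVA uses the Day 5 sample nearest 08:00 PM (SAP 12.6.2.2).
- Vital signs and ECG are descriptive. Smoking within 15 minutes of a vital-signs measurement is recorded (Protocol 7.4.8), and the ECG baseline is Screening (SAP 12.6.4.5.5), when smoking is allowed.
- Banked blood has no analysis in the SAP, and its Day 0 draw has no before-smoking condition either (Table 9).

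**Conclusion.** The gap is real and narrow. Nothing in either document requires the Day 6 nicotine/cotinine draws to come before smoking, and a cigarette smoked first by a THS 2.2 subject raises that subject's C_avg by one twelfth of the excess at 24 h. The numerical sizes rest on assumed excesses, an assumed affected fraction, and the general smoking hours applying on Day 6. How many subjects could be affected depends on how the completeness rule in SAP 7.2 is read. The SA Day 6 value can be wholly affected, but it enters only listings, summaries and graphs. The point does not threaten the study's success criterion. It merits correction because it touches a secondary comparison and costs almost nothing to close.

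**What to change.** Reconcile Protocol 4.1, 6.6.1, 7.5.1.2 and Table 15 so that the Day 6 nicotine/cotinine samples, in all arms, are taken before any conventional cigarette is dispensed. A before-smoking note on that row of Table 15, matching the notes on the CYP2A6 and spirometry rows, does most of the work. The synopsis and SAP 6.1 should then agree. No procedure is added. The cost is a longer wait on Day 6: until the 24-hour draw for late starters, and until the 08:00-10:00 AM draw in the SA arm.

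If the study is already running, use the dispensing times that Protocol 6.5.1 requires on each day of confinement to flag 24-hour samples drawn after a Day 6 cigarette. Report C_avg with and without the flagged subjects. Do not delete single 24-hour values: under SAP 7.2 a missing sample makes C_avg missing, and on its wording C_peak and t_peak as well. The analysis without flagged subjects will tend to drop late starters, so it should stand beside the full analysis and not replace it.

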**Table 1 Measured aerosol fractions for the THS Tobacco Sticks**

| Constituent (mg/THS Tobacco Stick) | ISO ¹ | Health Canada Intense regime ² |
|------------------------------------|------------------|---|
| Tar/NFDPM | 4 | 10.3 |
| Nicotine | 0.5 | 1.32 |
| Carbon monoxide | 1 | 0.6 |

¹ International Organization for Standardization ISO machine-smoking regimen. The analytical method has been modified to avoid inaccuracies as a result of condensation from high water-content aerosols.

² Health Canada Intense machine-smoking regimen (55 mL puff volume, 2-second puff duration, 30-second inter-puff interval) (Health Canada, 1999)

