12.6.1 Primary Analyses

12.6.1.1 Primary Biomarkers of Exposure in 24 hour collection

The primary BoExp (COHb in blood and urinary concentrations adjusted for creatinine of MHBMA, 3-HPMA and S-PMA) will be summarized as detailed in Section 12.1.3 “Descriptive Statistics”.

The baseline is as defined in Section 12.1.4 “Definitions for Statistical Data Analysis”,

The values and percent changes in the concentration adjusted for creatinine will be listed and summarized along with the COHb concentrations and percent changes from baseline. In addition line graphs will be produced for means (and 95% CI) over all timepoints.

For all arms the 24 hour urine collection will be collected daily from Day -1 to Day 5. Although the 24 hour urine collection will span into the following Day it will be reported by the day the collection started.

The primary endpoints will be log-transformed (base_e) prior to analysis. The analysis will compare (1) last Day 5 values of COHb in blood and (2) urinary concentrations of MHBMA, 3-HPMA and S-PMA corrected for creatinine on Day 5 between the THS 2.2 and CC arms. An ANCOVA (**Snedecor and Cochran 1982**) model will be used with terms for the log-transformed baseline value, sex, average daily CC consumption over the last 4 weeks as reported during screening and product.

The SAS code to be used is shown below:

```
Proc mixed data=_data_;
  Class product sex cigarette_cons;
  Model log (Day 5) = log (baseline) sex cigarette_cons product;
  Lsmean product / pdiff =control('CC') alpha=0.05 cl;
  Run;
```

The least squares (LS) means and estimate of the difference along with it's 95% CI will be back-transformed before presenting in the tables. The geometric LS means for each product along with the ratio (THS 2.2 : CC) and 95% CI will be presented in the tables.

The primary analysis will be performed on the FAS, with the PP Population used only to examine the robustness of the analysis of the primary endpoints.

In addition line graphs will be produced for product means (and 95% CI) over all timepoints for COHb in blood and urinary concentrations adjusted for creatinine of MHBMA, 3-HPMA and S-PMA.

The data will be presented in the below outputs, the TFL number refers to the TFL number in the accompanying TFL shell document:

TFL number	Title
FIGURES	
15.1.1.1	Blood COHb (%) Mean and 95% CI– FAS
15.1.1.2	MHBMA Urinary Concentration Adjusted for Creatinine (units) Mean and 95% CI – FAS

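### The Day 5 smoke-first exception, made for the nicotine profile, is worded so that it can also cover the evening COHb draw that is a primary endpoint

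*Protocol*

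**What the plan says.** Protocol 6.6.1 sets the ordinary order: "In general, the performance of scheduled procedures has priority over the wish of a subject to smoke". It then departs from it: "However, this is different on Day 5 due to the assessment of the nicotine profile". The operative sentence is "If the subject wants to smoke on Day 5 around the time of the blood draw, he/she should inhale/smoke first", with blood taken afterwards. It names both Tobacco Sticks and CC, and neither limits itself to nicotine tubes nor exempts COHb.

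The rule appears once more, in Protocol 7.5.1.2 on plasma nicotine and cotinine: "At all time points, if the subject wants to smoke around the time of the blood draw, he/she should smoke first". Protocol 7.5.1.1, on exhaled CO and COHb, has no such rule and refers to Section 9 for timing. The Section 9 time schedules do not order the evening COHb draw relative to product use.

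The primary analysis (SAP 12.6.1.1) takes "last Day 5 values of COHb in blood". Protocol Table 14 puts that sample at 08:00-10:00 PM. Baseline COHb is the Day 0 evening sample, which Table 9 puts in the same clock window but which falls under the ordinary order.

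**The concern.** A sampling rule written for one analyte may decide how a primary endpoint for another is sampled, on the endpoint day only. Two things are at stake.

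- **Comparability over time.** If the rule is applied to COHb, Day 5 is drawn after product use for those who want it, while on Days -1 to 4 the draw has priority. The COHb time course and the percent change from baseline would then mix a product effect with a change in sampling order.
- **The between-arm ratio.** COHb is the marker closest to the 50% margin, and success requires all four markers. If COHb rises proportionately more after a cigarette than after a Tobacco Stick, sampling just after use lowers the THS 2.2:CC ratio, towards success.

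The Protocol controls recency of use elsewhere. The first Day 5 COHb sample in the product arms must precede first use (7.5.1.1), and vital signs must record smoking in the preceding 15 minutes (7.4.8). The evening COHb sample has neither safeguard.

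**Working it through.** **1. Do the two draws meet?** In 7.5.1.2, "An additional 8 blood samples will be drawn in 2 hour intervals after T0", ending by 11:00 PM. A first use at 06:30 AM puts a nicotine draw at 08:30 PM; 07:30 AM puts one at 09:30 PM. Two-hourly draws therefore normally place one inside the two-hour COHb window. Neither document says whether COHb is drawn with it, or before or after product use.

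**2. The plan's own power figure.** Inputs are COHb ratio 0.40 (CV 0.32) and 0.44 (CV 0.14) from Protocol Tables 16 and 17, n = 80 and 40, one-sided 2.5%, margin 0.50.

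- log-SD = sqrt(ln(1 + CV²)) = 0.312 and 0.139
- SE = log-SD × sqrt(1/80 + 1/40) = 0.060 and 0.027
- COHb power (noncentral t, 118 df) at ratio 0.40, CV 0.32 = 95.5%

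Table 18 states 96% for all four markers jointly. The other three each have power of at least 99.3% by the same method, so COHb drives study power. To pass, the observed COHb ratio must be below about 0.444 (CV 0.32) or 0.474 (CV 0.14).

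**3. Relative rise in THS 2.2 against CC.** The documents give no acute rise for either product. Table 16 gives THS 2.2/CC = 0.40 and THS 2.2/SA = 2.10. Taking CC as 1 and SA as background:

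- SA = 0.40/2.10 = 0.190
- product-attributable share in CC = 1 - 0.190 = 0.81
- product-attributable share in THS 2.2 = (0.40 - 0.190)/0.40 = 0.52
- relative rise in THS 2.2 as a fraction of that in CC = 0.52/0.81 ≈ 0.65

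This assumes that the rise after one product scales with the product-attributable share.

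**4. Shift in the ratio.** Let c be the relative rise in CC and f the share of subjects in each product arm who smoke first because of the rule. Both are assumptions. The geometric mean ratio is multiplied by k = [(1 + 0.65c)/(1 + c)]^f.

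| c | f | k | Fall in ratio | Type I error at true 0.50, CV 0.32 | CV 0.14 |
|---|---|---|---|---|---|
| none | none | 1 | 0 | 2.5% | 2.5% |
| 5% | 25% | 0.9958 | 0.4% | 2.9% | 3.5% |
| 10% | 50% | 0.984 | 1.6% | 4.5% | 8.6% |
| 15% | 75% | 0.9656 | 3.4% | 8.3% | 25% |

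The last two columns are for COHb alone and take the ratio under the ordinary order as the true one.

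**5. At the planned ratios.** Multiplying by k = 0.9958 to 0.9656 takes 0.40 to 0.398-0.386 and 0.44 to 0.438-0.425. Both lie below 0.50 with or without the rule.

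**The case against.** The strongest reply is that the exception is for nicotine draws only. Its stated reason is the nicotine profile, its only restatement is in the nicotine section, and the COHb section does not contain it. That is a fair reading of intent. It does not remove the problem, because 6.6.1 is the general restriction that site staff follow, and its wording leaves open how a primary endpoint is drawn.

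Other points stand in whole or part:

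- **Both product arms are covered.** Only a difference in relative rise moves a ratio; with equal rises k = 1. A reader might infer from Table 1, where a Tobacco Stick yields at most 1 mg CO, that the rise occurs essentially in CC alone. Setting the THS 2.2 rise to zero gives k = (1 + c)^-f and a fall of 1.2-10% for the same c and f. The documents do not support this: Table 1 gives no CC yield, and the planning ratios suggest a THS 2.2 relative rise about 0.65 of that in CC.
- **f may be smaller.** Smoking is allowed for 990 minutes a day. At 20 CC/day the mean gap is about 50 minutes; at 10/day, about 99. If the wish to smoke must fall in a 10-minute span (the nicotine draws have ±5 minutes), f is about 10-20%. With c of 5-15% and the 0.65 factor, the fall is then 0.2-0.9%, and type I error at most about 3.5% (CV 0.32) or 5.3% (CV 0.14).
- **Which order is the right reference is open.** In an ad libitum study, drawing first may delay a wanted cigarette. That argues for one stated order on every day, not for a switch on Day 5.
- **The Day 0 mismatch does not bias the primary contrast.** A reader might infer that it does. But on Day 0 all subjects smoked CC and did not know their arm, so baseline was sampled alike in every arm.
- **A partial check exists.** SAP Section 9 plans COHb least squares means at each time point, where a Day 5 step might show. It would not separate sampling order from a real change.

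**Conclusion.** The point holds as an ambiguity in 6.6.1 that can affect a primary endpoint. Followed literally, the exception makes Day 5 COHb not comparable with Days -1 to 4, and may move the THS 2.2:CC ratio towards success.

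The documents do not establish that the rule does govern the COHb sample, or that the ratio is in fact shifted. The direction depends on a smaller relative rise in THS 2.2 than in CC, which the planning ratios suggest but do not show. The size rests on assumed values of c and f and on the inferred 0.65. Over the ranges used, the fall is about 0.4-3.4%, with COHb type I error at a true ratio of 0.50 of about 2.9-8.3% (CV 0.32) or 3.5-25% (CV 0.14). It is smaller if fewer subjects smoke first. Since the planned ratios are below 0.50 either way, this is an inexpensive correction worth making, not a flaw that by itself undermines the trial.

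**What to change.** In Protocol 6.6.1, limit the Day 5 exception to the nicotine and cotinine samples, so that COHb and its paired CO breath test follow the same order on Day 5 as on Days -1 to 4. This costs one sentence and an occasional COHb tube drawn separately from the nicotine tube; the two-hour window leaves room for it.

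If the data are already collected, use the dispense and return times that Protocol 6.5.1 requires to tabulate time since last product use at the evening COHb draw, by arm, on Day 0 and Day 5. Report, as supportive, the Day 5 evening COHb ratio beside the Day 4 evening ratio. Day 4 is a topography-device day in both product arms (Protocol 7.8.1), so showing Day 3 as well would help. This uses data already recorded.

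Do not exclude draws taken soon after use: that selects on behaviour after randomization and could lower the CC mean by removing frequent smokers.
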